5.3. Lifestyle Considerations

Potential participants must be willing and able to adhere to the following lifestyle restrictions during the study to be eligible for participation:

- 1. refer to Section 6.8, Concomitant Therapy for details regarding prohibited and restricted therapy during the study.
- 2. agree to follow all requirements that must be met during the study as noted in the Inclusion and Exclusion Criteria.

5.4. Screen Failures

Participant Identification, Enrollment, and Screening Logs

The investigator agrees to complete a participant identification and enrollment log to permit easy identification of each participant during and after the study. This document will be reviewed by the sponsor study-site contact for completeness.

The participant identification and enrollment log will be treated as confidential and will be filed by the investigator in the study file. To ensure participant confidentiality, no copy will be made. All reports and communications relating to the study will identify participants by participant

identification and age at initial informed consent. In cases where the participant is not randomized into the study, the date seen and age at initial informed consent will be used.

Rescreening is allowed only for resolution of an acute condition or meeting a time window (eg, for a prohibited medication). Only 1 rescreening per participant is permitted. Rescreened participants will be assigned a new participant number, undergo the informed consent process, and then restart a new screening phase.

5.5. Criteria for Temporarily Delaying Study Vaccine Administration

The following events constitute a temporary contraindication to study vaccination:

- Clinically significant acute illness at the time of vaccination. This does not include minor illnesses, such as diarrhea or mild upper respiratory tract infection.
- Fever (body temperature ≥38.0°C [≥100.4°F]) within 24 hours prior to the planned time of vaccination.

If any of these events occur at the scheduled time for vaccination, randomization at a later date within the screening window (allowed window up to 10 days) is permitted at the discretion of the investigator and after consultation with the sponsor. If randomization cannot occur within the screening window, rescreening is required.

If the vaccination visit cannot be rescheduled within the allowed window or the contraindications to vaccination persist, the sponsor should be contacted for further guidance.

6. STUDY VACCINE(S) AND CONCOMITANT THERAPY

6.1. Study Vaccine Administration

The investigational medicinal products (IMPs) to be administered to participants in this study are Ad26.RSV.preF and RSV preF protein.

The Ad26/protein preF RSV vaccine to be used in this study is composed of Ad26.RSV.preF and RSV preF protein, to be administered as a single injection (1.0 mL) in the deltoid muscle:

- Ad26.RSV.preF (JNJ-64400141) will be used at a dose level of 1.0×10^{11} viral particles (vp) in Group 1, 2.5×10^{10} vp in Group 2, and 1.0×10^{10} vp in Group 3.
- RSV preF protein (JNJ-64213175) will be used at a dose level of 150 µg in all groups (Groups 1 to 3). Three different lots will be used (a release lot; an aged lot representing the presumed end of shelf-life; and an aged lot representing the intermediate shelf-life).

Ad26.RSV.preF and RSV preF protein will be manufactured and provided under the responsibility of the sponsor. Labels will contain information to meet the applicable regulatory requirements. Note that RSV preF protein will be labelled as "RSV-F Vaccine". Refer to the IB for Ad26/protein preF RSV vaccine for details on the components and a list of the excipients (IB Ad26/protein preF RSV vaccine 2021).

Participants will be vaccinated at the study site according to the schedule shown in Table 2. On Day 1, each participant will receive an IM injection of Ad26/protein preF RSV vaccine.

Study vaccine administration must be captured in the source documents and the electronic case report form (eCRF).

For a definition of study vaccine overdose, refer to Section 6.7.

6.2. Preparation/Handling/Storage/Accountability

Preparation/Handling/Storage

Vials must be stored in a secured location under controlled temperature with no access for unauthorized personnel. The study refrigerator/freezer must be equipped with a continuous temperature monitor and alarm and should be equipped with back-up power systems. If the study vaccine components are exposed to temperatures outside the specified temperature range, all relevant data will be sent to the sponsor to determine if the affected study vaccine components can be used or will be replaced. The affected study vaccine components must be quarantined and not used until further instruction from the sponsor is received.

An unblinded study-site pharmacist, or other qualified individual will prepare the appropriate vials and syringes, labeled with the participant's identification number, and provide the syringes for Ad26/protein preF RSV vaccine in a blinded manner to the blinded study vaccine administrator who will perform the injection.

Refer to the Investigational Product Preparation Instructions and Study Site Investigational Product and Procedures Manual for additional guidance on study vaccine preparation, handling, and storage.

Accountability

The investigator is responsible for ensuring that all study vaccine received at the site is inventoried and accounted for throughout the study. The study vaccine administered to the participant must be documented on the vaccine accountability form. All study vaccine will be stored and disposed of according to the sponsor's instructions.

Study vaccine must be handled in strict accordance with the protocol and the container label, and must be stored at the study site in a limited-access area or in a locked cabinet under appropriate environmental conditions. Unused study vaccine must be available for verification by the sponsor's study-site monitor during on-site monitoring visits. The return to the sponsor of unused study vaccine will be documented on the vaccine return form. When the study site is an authorized destruction unit and study vaccine supplies are destroyed on site, this must also be documented on the vaccine return form.

Potentially hazardous materials containing hazardous liquids, such as used ampules, needles, syringes, and vials, should be disposed of immediately in a safe manner and therefore will not be retained for vaccine accountability purposes.

Study vaccine should be dispensed under the supervision of the investigator or a qualified member of the study-site personnel. Study vaccine will be supplied only to participants participating in the study. Study vaccine may not be relabeled or reassigned for use by other participants. The investigator agrees neither to dispense the study vaccine from, nor store it at, any site other than the study sites agreed upon with the sponsor.

Refer to the Investigational Product Preparation Instructions and Study Site Investigational Product and Procedures Manual for additional guidance on the final disposition of unused study vaccines.

6.3. Measures to Minimize Bias: Randomization and Blinding

Study Vaccine Allocation

Procedures for Randomization

Central randomization will be implemented in this study. Participants will be randomly assigned to 1 of 3 groups based on a computer-generated randomization schedule prepared before the study by or under the supervision of the sponsor. The randomization will be balanced by using randomly permuted blocks. The interactive web response system (IWRS) will assign a unique study vaccine allocation code, which will dictate the study vaccine assignment and matching study vaccine kit for the participant. The requestor must use their own user identification and personal identification number when contacting the IWRS, and will then give the relevant participant details to uniquely identify the participant.

Blinding

The investigator will not be provided with randomization codes until database lock of the final analysis. The participants remain blinded until database lock of the final analysis. The codes will be maintained within the IWRS, which has the functionality to allow the investigator to break the blind for an individual participant.

For the sponsor, unblinding (at the participant level) will occur at the time of the primary analysis (Section 9.5). From the primary analysis onwards, group level results may be shared as needed, however, efforts will be made to preserve the blinding to the individual participant allocation.

Data that may potentially unblind the randomization group assignment (eg, immunogenicity data, study vaccine preparation/accountability data, study vaccine allocation) will be handled with special care to ensure that the integrity of the blind is maintained and the potential for bias is minimized. This can include making special provisions, such as segregating the data in question from view by the investigators, clinical team, or others as appropriate until the time of database lock and unblinding.

The investigator may in an emergency determine the identity of the randomization group by contacting the IWRS. While the responsibility to break the study vaccine allocation code in emergency situations resides solely with the investigator, it is recommended that the investigator contacts the sponsor or its designee if possible, to discuss the particular situation, before breaking the blind. Telephone contact with the sponsor or its designee will be available 24 hours per day, 7 days per week. In the event the blind is broken, the sponsor must be informed as soon as possible. The date, time, and reason for the unblinding must be documented by the IWRS, in the appropriate section of the eCRF, and in the source document. The documentation received from the IWRS indicating the code break must be retained with the participant's source documents in a secure manner.

The study-site pharmacist or qualified individual with primary responsibility for study vaccine preparation and dispensing will be unblinded to study vaccine allocation.

Participants who have had their randomization group assignment unblinded should continue to return for scheduled evaluations.

Participants who withdraw will not be replaced.

6.4. Study Vaccination Compliance

Study vaccine will be administered IM by blinded qualified study-site personnel at the study site. Details of each administration will be recorded in the eCRF (including date and time of injection, and site of administration). For blinding procedures, see Section 6.3.

6.5. Dose Modification

Not applicable.

6.6. Continued Access to Study Vaccine After the End of the Study

Participants will be instructed that study vaccine will not be made available to them after they have completed/discontinued study vaccination.

6.7. Treatment of Overdose

For this study, any dose of the Ad26/protein preF RSV vaccine greater than the protocol-specified dose will be considered an overdose. The sponsor does not recommend specific treatment for an overdose.

In the event of an overdose, the investigator or treating physician should:

- Contact the Medical Monitor immediately.
- Closely monitor the participant for AEs/SAEs/AESIs until resolution.
- Document the quantity of the excess dose in the eCRF.
- Report as a special reporting situation.

6.8. Concomitant Therapy

Prestudy therapies administered within the 30 days before administration of the study vaccine must be recorded on Day 1. Additionally, any history of SARS-CoV-2 vaccination (name/manufacturer of the vaccine and date of administration, whenever possible) prior to and during the study will be collected in the eCRF.

Concomitant therapies associated with solicited AEs will be collected by the participants in the participant diary from the time of study vaccination through 7 days after vaccination. Concomitant therapies associated with unsolicited AEs will be collected and recorded in the eCRF from the time of study vaccination through 28 days after vaccination. Concomitant therapies associated with SAEs or AESIs will be collected and recorded in the eCRF from ICF signature until 6 months after vaccination.

Analgesic/antipyretic medications and non-steroidal anti-inflammatory drugs may be used post-vaccination only in cases of medical need (eg, fever or pain) and their use must be documented. Use of these medications as routine prophylaxis prior to study vaccination is discouraged.

Information on concomitant use of herbal supplements or vitamins will not be collected.

Use of any experimental medication (including experimental vaccines other than the study vaccine) during the study is not allowed.

Vaccination with licensed live attenuated vaccines within 28 days of a study vaccination (ie, before or after) is prohibited. Other licensed (not live) vaccines (eg, influenza, tetanus, hepatitis A, hepatitis B, rabies) should be given at least 14 days before (or at least 14 days after) administration of study vaccine in order to avoid potential confusion of adverse reactions and potential immune interference. If a vaccine is indicated in a post-exposure setting (eg, rabies or tetanus), it must take priority over the study vaccine.

For SARS-CoV-2 vaccines licensed or available under Emergency Use Authorization: live attenuated vaccines should be given at least 28 days before or after vaccination; non-live vaccines should be given at least 14 days before or after vaccination. A viral-vectored SARS-CoV-2 vaccine is not to be given within 6 months prior to randomization or during the study period until 28 days after the last study vaccination.

Use of systemic corticosteroids^a must be documented until 14 days after study vaccination. Antineoplastic and immunomodulating agents, eg, cancer chemotherapeutic agents or systemic corticosteroids, or radiotherapy are prohibited until 14 days after study vaccination. If the use of systemic corticosteroids, antineoplastic or immunomodulating agents or any therapy described in

_

^a Note: Ocular, topical, or inhaled steroids are allowed.

exclusion criterion 7 becomes medically indicated during the study for any participant, the sponsor should be notified.

The sponsor must be notified in advance (or as soon as possible thereafter) of any instances in which prohibited therapies are administered.

7. DISCONTINUATION OF STUDY VACCINATION AND PARTICIPANT DISCONTINUATION/WITHDRAWAL

7.1. Discontinuation of Study Vaccination

A participant's study vaccination must be discontinued if:

- The participant withdraws consent to receive study vaccination.
- The investigator believes that for safety reasons or reactogenicity reasons (eg, AE) it is in the best interest of the participant to discontinue study vaccination.

Study vaccine assigned to the participant who discontinued study vaccination may not be assigned to another participant. Discontinuation of study vaccination is only possible between screening and vaccination.

7.2. Participant Discontinuation/Withdrawal From the Study

A participant will be withdrawn from the study for any of the following reasons:

- Lost to follow-up
- Withdrawal of consent
- Death
- Any AE that requires discontinuation from the study
- Repeated failure to comply with protocol requirements

When a participant withdraws before study completion, the reason for withdrawal is to be documented in the eCRF and in the source document. If the reason for withdrawal from the study is withdrawal of consent then no additional assessments are allowed.

An early exit visit (by telephone) will be conducted for those participants who are unable to continue participation in the study and withdraw from the study before Day 183, but who do not withdraw consent (see Schedule of Activities). Participants who wish to withdraw consent from participation in the study will be offered an early exit visit (prior to formal withdrawal of consent; by telephone). They have the right to refuse.

Withdrawal of Consent

A participant declining to return for scheduled visits does not necessarily constitute withdrawal of consent. Alternate follow-up mechanisms that the participant agreed to when signing the ICF apply

(eg, consult with family members, contacting the participant's other physicians, medical records, database searches, use of locator agencies at study completion) as local regulations permit.

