1.3. Schedule of Activities

Clinic Visit #	1ª	2	3 b 🕿	4	5 b 🕿	6	Exit b,c
Visit Timing		Vac	Vac	Vac	Vac	Vac	
Visit I lilling		vac	+ 7 d	+ 14 d	+ 28 d	+ 6 mo	
Visit Day	-28 to 1	1	8	15	29	183	
Visit Window			±2 d	-3 d / +7 d	±7 d	±14 d	
Visit Type	SCREENING	VACCINATION	Safety	Immunogenicity and Safety	Safety	Immunogenicity and Safety	Early exit
Written informed consent d	•						
Inclusion/exclusion criteria	•	0					
Demographics	•						
Medical history e/prestudy therapies f	•						
Vital signs g including body temperature	•	0					
Height and weight	•						
Randomization		0					
Pre-vaccination symptoms h		0					
Humoral immunity, mL		0 ° 10		●° 10		●° 10	
Vaccination		•					
15-minute post-vaccination observation i		•					
Solicited AE recording ^p			8				4
Unsolicited AE recording q					6		
SAE recording						•	
AESI recording j				continuous-			•
Concomitant therapies k			•				
History of SARS-CoV-2 vaccination 1							
Participant diary distribution m,n							
Participant diary (collection and) review by site staff n				•			
Approximate daily blood draw, mL		10	_	10	_	10	_
Approximate cumulative blood draw, mL		10	10	20	20	30	_

• pre-vaccination; • pre- and post-vaccination; • solicited local (injection site) and solicited systemic AEs will be collected via participant diaries from vaccination until 7 days post-vaccination; • if within 7 days of vaccination; • if the early exit visit is within 28 days of vaccination.

Note: At any clinic visit, an abbreviated, symptom-directed physical examination may be performed if deemed necessary by the investigator based on any clinically relevant issues, clinically relevant symptoms, and medical history.

Footnotes:

- a. Screening will be performed within 28 days prior to the study vaccination or on the day of vaccination. If screening is performed on the day of vaccination (recommended), Visit 1 and Visit 2 will coincide on Day 1. In that case, assessments should only be done once. Screening must be completed and all eligibility criteria must be fulfilled prior to randomization and vaccination.
- b. Safety visits and early exit visit will be by telephone.

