8.3.1. Time Period and Frequency for Collecting AE, SAE, and AESI Information

All AEs

AEs and special reporting situations, whether serious or non-serious, that are related to study procedures or that are related to non-investigational sponsor products will be reported from the time a signed and dated ICF is obtained until the end of the study/early withdrawal.

Clinically relevant medical events not meeting the above criteria and occurring between signing of ICF and moment of vaccination will be collected on the Medical History eCRF page as pre-existing conditions.

Solicited AEs, collected through a participant diary, will be recorded from the time of vaccination until 7 days post-vaccination.

All other unsolicited AEs and special reporting situations, whether serious or non-serious, will be reported from the time of vaccination until 28 days post-vaccination.

All SAEs and AEs leading to discontinuation from the study (regardless of the causal relationship) are to be reported from the moment of vaccination until completion of the participant's last study-related procedure, which may include contact for safety follow-up. The sponsor will evaluate any safety information that is spontaneously reported by an investigator beyond the time frame specified in the protocol.

See Section 7.2 for procedures associated with withdrawal of consent.

All AEs will be followed until resolution or until clinically stable.

SAEs

All SAEs occurring during the study must be reported to the appropriate sponsor contact person by study-site personnel immediately, but no later than 24 hours of their knowledge of the event.

Information regarding SAEs will be transmitted to the sponsor using the SAE Form and Safety Report Form of the eCRF, which must be completed and reviewed by a physician from the study site, and transmitted to the sponsor immediately but no later than within 24 hours. The initial and follow-up reports of an SAE should be transmitted electronically or by facsimile (fax). Telephone

reporting should be the exception and the reporter should be asked to complete the appropriate form(s) first.

AESIs

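### Section 7.2 withdraws consenting participants after the single dose for certain AEs or repeated non-compliance, and no passage says their 6-month safety contact or later blood samples continue

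*Protocol*

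**What the plan says.** Protocol 7.2 introduces its list with "A participant will be withdrawn from the study for any of the following reasons". The list includes "Any AE that requires discontinuation from the study" and "Repeated failure to comply with protocol requirements". Withdrawal of consent is a separate item, so these two reasons apply to people who still consent. No criterion says which AE qualifies.

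There is no further treatment to stop. Protocol 6.1 says "On Day 1, each participant will receive an IM injection of Ad26/protein preF RSV vaccine", and Protocol 7.1 says "Discontinuation of study vaccination is only possible between screening and vaccination".

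After withdrawal the plan provides an early exit contact. Footnote b of the Schedule of Activities (Protocol 1.3) says "Safety visits and early exit visit will be by telephone", and the schedule shows blood draws on Days 1, 15 and 183 only.

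Protocol 8.3.1 has SAEs, and AEs leading to discontinuation from the study, reported from vaccination "until completion of the participant's last study-related procedure, which may include contact for safety follow-up". The Synopsis (Safety Evaluations) applies the same limit to AESIs. The AESI paragraph of 8.3.1 and footnote j of the Schedule instead give 6 months after vaccination and do not mention withdrawn participants.

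SAP 5.1.2 (Table 3) ends the follow-up phase at the date of last contact, and Table 4 cuts the AESI intervals in the same way. SAP 5.5.1.4 treats anyone who reports no event as not having had one.

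Unblinded participants are handled differently. Protocol 6.3 says "Participants who have had their randomization group assignment unblinded should continue to return for scheduled evaluations".

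**The concern.** In a multi-dose trial, withdrawal for an AE may serve to stop exposure. Here all exposure is complete on Day 1, so withdrawal removes only observation, and it does so in people who had a notable AE or complied poorly. SAEs and AESIs to 6 months are a secondary endpoint, and pre-F ELISA and neutralizing titers at 6 months are exploratory endpoints. Both lose data under this rule.

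The SAP's counting rule adds to the problem. Unsolicited-AE percentages use the number of participants in the phase as denominator, not follow-up time (SAP 5.5). Someone withdrawn early in the post-dose period therefore stays in that denominator and counts as event-free for days when nobody asked. The Ad26 dose differs 10-fold between Groups 1 and 3, so AE-related withdrawals need not be equal across groups, although the documents give no rates. Events that were never collected cannot be recovered by analysis.

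**Working it through.** **1. What continues after withdrawal with consent intact.**

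| Item | Text that limits it | Text that might keep it |
|---|---|---|
| Day 15 and Day 183 samples | Exit visit by telephone; no draw in the exit column (1.3, 7.2) | None found for these participants |
| New SAEs | Last study-related procedure (8.3.1; Synopsis) | Safety contact may count as that procedure, but none is scheduled after exit |
| New AESIs | Last study-related procedure (Synopsis) | 6 months (8.3.1; 1.3 footnote j), again with no contact scheduled after exit |
| AEs already reported | None | Followed until resolved or stable (2.3.3, 8.3.1); unresolved SAEs followed after discontinuation (10.2.5) |
| Analysis | Phases and intervals end at last contact (SAP 5.1.2) | None |

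The gap is therefore new SAEs and later samples. For AESIs it is an unresolved contradiction.

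**2. Follow-up lost per withdrawn participant.** The horizon is Day 1 to Day 183, or 182 days. The share lost is (183 − withdrawal day)/182:
- Day 8: 175/182 = 96%
- Day 15: 168/182 = 92%
- Day 29: 154/182 = 85%

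Protocol 2.2 puts symptom onset of thrombosis with thrombocytopenia syndrome (TTS), seen with the Janssen COVID-19 vaccine, at about 1 to 2 weeks, roughly Days 8 to 15. A Day 8 withdrawal would miss most of that period.

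These are per-person figures on chosen days. As an assumption, if 1 to 5 of 250 per group were withdrawn on Day 8, the group would lose (1/250) × 0.96 = 0.4% to (5/250) × 0.96 = 1.9% of its planned follow-up.

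**3. Primary comparison: reproducing the plan's figure.** Inputs from Protocol 9.2: true GMR 0.9, margin 2/3, SD 1.3 on the log2 scale, two-sided alpha 5%, power 95%.
- Distance to the margin: log2(0.9/(2/3)) = log2(1.35) = 0.433.
- n = 2 × 1.3² × (1.960 + 1.645)² / 0.433² ≈ 234.3, so 235 by the normal formula. The noncentral t version gives 0.9498 at 235 and 0.9506 at 236, so the stated 236 reproduces.
- Power = Φ(0.433/(1.3 × √(2/n)) − 1.96). Joint power for both comparisons uses a bivariate normal with correlation 0.5.

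| Evaluable per group | Power per comparison | Joint power |
|---|---|---|
| 236 (plan) | 95.1% | 91.4% |
| 225 (10% loss, assumed) | 94.2% | 89.9% |
| 220 (12% loss, assumed) | 93.7% | 89.1% |

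The allowance for all losses is 250 − 236 = 14 per group (14/250 = 5.6%). Of the withdrawals at issue, only those before the Day 15 sample use it.

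**4. Primary comparison: illustrative bias.** Suppose a fraction p of Group 1 alone is lost before Day 15, and those participants would have been d SDs above the mean. The Group 1 mean then falls by p × d × 1.3/(1 − p) on the log2 scale.
- p = 0.02, d = 0.5: 0.02 × 0.5 × 1.3/0.98 = 0.0133, so the GMR is multiplied by 2^0.0133 = 1.009.
- p = 0.03, d = 1: 0.03 × 1 × 1.3/0.97 = 0.0402, so the GMR is multiplied by 2^0.0402 = 1.028.

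With equal loss in all groups the shift is close to zero.

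**The case against.** The best defence is that the end of follow-up is pieced together from several passages and not stated in one place. Section 7.2 bars further assessments only when consent is withdrawn. The reporting window may include safety contact, reported AEs are followed to resolution, and the sponsor evaluates late spontaneous reports. After a missed visit, Section 7.3 asks sites to reschedule and to establish whether the participant wishes to or should continue. This is true, and it makes the defect a gap plus a contradiction, not an explicit ban. It does not close the gap. Following a known event is not asking about new ones, and a permitted contact is not a scheduled one. The alternate follow-up routes in 7.2 are written for participants who decline visits, not for those the site withdraws.

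Three stronger readings are tempting, and the documents do not support them.
- A reader might infer that any AE leads to withdrawal. The rule covers only an AE that requires discontinuation. That wording is circular, but it is narrower.
- A reader might infer that AESI collection clearly stops at exit. Section 8.3.1 and footnote j say 6 months, so the documents conflict.
- A reader might infer that the rule biases the primary result towards non-inferiority. That needs 2–3% of Group 1 (5 to 8 people) lost before Day 15, no such loss in the other groups, and above-average titers in those lost. No passage supplies any of these. Section 2.3.1 describes solicited AEs as mild to moderate and short-lived. Section 4.3 reports similar reactogenicity across the regimens in the earlier dose-selection study, although the combination groups it describes do not include this trial's two lower doses.

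It is also fair to say that an investigator may have good reason to stop a procedure in a given person. The fix should leave that judgment in place.

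**Conclusion.** The point stands in limited form. After the Day 1 dose, Section 7.2 requires withdrawal of some consenting participants, and nothing in the protocol or SAP keeps them in new-SAE collection or scheduled sampling. For AESIs, the Synopsis must be reconciled with Section 8.3.1 and footnote j. The loss falls on the 6-month SAE/AESI endpoint and the Day 183 titers. Per person it is large (85% to 96% of follow-up for withdrawal between Day 29 and Day 8). In total it cannot be sized, because the documents give no expected number of such withdrawals, and it may be small.

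The effect on the Day 15 comparison is likely small. Power per comparison is still 94.2% at an assumed 10% loss, and the 0.9% to 2.8% GMR shift only illustrates a one-sided scenario. The conclusion assumes that a participant withdrawn by the site gets the exit call and no other scheduled contact, which is the natural reading of the schedule but is not stated outright.

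**What to change.** Amend Protocol 7.2 so that, after vaccination, a participant who meets the AE or non-compliance reason but keeps consent and can be reached:
- continues SAE/AESI telephone contact to 6 months; and
- is offered the scheduled Day 15 and Day 183 samples, unless the investigator judges a procedure inappropriate for that participant.

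Reconcile the AESI collection window in the Synopsis with Section 8.3.1 and footnote j of the Schedule of Activities, stating what applies to withdrawn participants.

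The cost is protocol wording, a few extra calls and visits that are already scheduled. The sample size and the primary analysis do not change.
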